## 7.4 Exploratory outcome analyses

The effect of the intervention on exploratory outcomes will be assessed using the same models as used for the secondary outcomes.

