#### 4.3 Sample size

The recent rasagiline for MSA (MSA-Ras) trial evaluated rasagiline versus placebo using the UMSARS total (Parts I and II) as the primary efficacy measure after 48 weeks treatment. Patients in the placebo group declined by mean 7.8 points (SD 10.4 – Werner et al. 2015).

Therefore, on the basis of this previously collected data and with a two-sided 5% significance level, we estimated that a sample size of 40 patients (20 per group) would be required to detect a difference of 5 total UMSARS points between the two groups, assuming a correlation between baseline and final disease severity of 0.85. These calculations were based on a common SD of 10.4, 80% power and an

overall type 1 error rate of 5%. A 5-point difference between groups would be a clinically important effect size. Based on a 20% dropout rate as reported from previous trials, the sample size would be 50 (25 per arm).

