## 7.2 Primary outcome Analysis

The primary outcome is the total Unified Multiple System Atrophy Rating Scale (UMSARS) score (Parts I and II) at 48 weeks. The primary analysis will compare exenatide patients to be best medically treated patients using a two-level mixed model that includes the total UMSARS scores from four time-points (12 weeks, 24 weeks, 36 weeks and 48 weeks) with interaction terms between the intervention and time-point indicator variables to enable estimation of the effect of intervention at 48 weeks. This model will also adjust for baseline UMSARS score and MSA subtype using fixed effects.

In detail, the primary analysis will involve fitting the model

$$UMSARS_{ij} = \beta_0 + \beta_1 TRT_i + \beta_2 j TIME_j + \beta_3 j TRT_i \times TIME_j + \beta_4 UMSARS0_i + \beta_5 MSA_i + u_i + \epsilon_{ij}$$

to patients  $i = 1, \dots, 48$  and time-points  $j = 12, 24, 38$  and 48 weeks, where  $UMSARS_{ij}$  and  $UMSARS0_i$  are the UMSARS total scores for patient  $i$  at time-point  $j$  and baseline respectively,  $TRT_i$  is the intervention group indicator (0=standard; 1=Exenatide),  $TIME_j$  are time-point indicators,  $MSA_i$  is a MSA subtype indicator, and  $u_i \sim N(0, \sigma_u^2)$  and  $\epsilon_{ij} \sim N(0, \sigma^2)$  are error terms. All modelling assumptions will be checked.

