## 7.3 Secondary outcome analyses

The effect of the intervention on secondary outcomes will be assessed using appropriate single-level regression models, i.e. linear regression models for numerical outcomes, logistic regression models for binary outcomes, and Poisson models for count outcomes (or negative binomial models, if their use is indicated). All models will be adjusted for MSA subtype; models for numerical outcomes will also be adjusted for baseline outcomes if available. All analyses of secondary and other outcomes should be considered as supportive analyses.

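### Week-96 UMSARS I+II is analysed by single-level regression that leaves the week 12 to 48 scores unused, with no committed method to recover them

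*SAP*

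**What the plan says.** - **Week 48, primary.** SAP 7.2 compares the arms on UMSARS I+II with a "two-level mixed model that includes the total UMSARS scores from four time-points" (weeks 12, 24, 36 and 48), a random patient intercept, baseline score and MSA subtype.
- **Secondary outcomes.** SAP 7.3 uses "appropriate single-level regression models, i.e. linear regression models for numerical outcomes", adjusted for subtype and, for numerical outcomes, for baseline. It calls analyses of secondary and other outcomes supportive.
- **Week 96, exploratory.** SAP 7.1.3 lists UMSARS I+II at 96 weeks. SAP 7.4 says: "The effect of the intervention on exploratory outcomes will be assessed using the same models as used for the secondary outcomes".
- **Visits.** SAP Table 1 schedules all parts of UMSARS, and MoCA, at weeks 0, 12, 24, 36, 48 and 96. MSA-QoL is scheduled at 0, 48 and 96 only. CGI does not appear in the table.
- **Missing data.** SAP 7.5 limits the sensitivity analyses to the primary outcome. In SAP 7.7 the analysis that adds predictors of missingness is tied to the primary model. Multiple imputation, with an imputation model drawing on all time-points, is permitted if thought appropriate, and no outcome is named for it.

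**The concern.** The SAP chooses a longitudinal model for UMSARS I+II at week 48 and drops it for the same scale at week 96, where cumulative loss can only be equal or greater. As written, the week-96 fit uses the baseline and week-96 scores alone.

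That matters if patients who are seen to worsen are more likely to be absent later. Those who remain in each arm are then a selected group, and baseline and subtype do not explain the selection, whereas the unused interim scores do.

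Treatment lasts 48 weeks, and week 96 is the only efficacy visit after it. It is therefore the only result that bears on persistence of effect, a feature that Protocol section 3 highlights from the earlier open-label Parkinson's disease trial. Protocol 5.1 also intends the results to support funding and sample size for a larger trial, so a distorted estimate would be carried forward.

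**Working it through.** **1. What the stated fits use (SAP 7.2 to 7.4, Table 1)**

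| Analysis of UMSARS I+II | Visits used | Recorded follow-up visits not used |
|---|---|---|
| Week 48, primary | 0, 12, 24, 36, 48 | none up to week 48 |
| Week 96, exploratory | 0, 96 | 12, 24, 36, 48 |

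**2. The plan's own figure, and what it says about the SD**

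Inputs from SAP 4.3: "with a two-sided 5% significance level"; "common SD of 10.4, 80% power"; a sample to "detect a difference of 5 total UMSARS points between the two groups"; "assuming a correlation between baseline and final disease severity of 0.85"; 20% dropout.

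- Residual SD = 10.4 × √(1 − 0.85²) = 5.48.
- n per arm = 2 × (1.960 + 0.842)² × 5.48² / 5² = 18.85, so 19 by normal approximation. A noncentral t calculation gives 80.2% power at 20 per arm.
- 40 / (1 − 0.20) = 50.

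The sample size reproduces and is not in question. It does leave two readings of 10.4. As a common SD with correlation 0.85, it implies an SD of change of 10.4 × √(2 × (1 − 0.85)) = 5.7. As the SD given where "Patients in the placebo group declined by mean 7.8 points", it is itself the SD of change. Both are carried forward.

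**3. Simulation inputs**

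- From the documents: decline of 7.8 points per 48 weeks, SD as above, 50 patients allocated 1:1, the visit schedule, and a 5-point effect.
- Assumed: linear progression with random slopes; residual SD 3; the effect at week 96; dropout that, once it occurs, is permanent and has log-odds rising with the last observed worsening; and the dropout rate at week 96. The documents give neither that rate nor a mechanism.

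**4. Estimated week-96 difference (negative favours exenatide)**

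| Setting | Single-level, change SD 5.7 | Single-level, change SD 10 to 10.4 | Longitudinal likelihood model |
|---|---|---|---|
| Same mechanism, true −5; about 11–13% missing at week 48 and 23–28% at week 96 | −4.8 to −4.7 | −4.3 to −3.6 | −5.1 to −4.9 |
| Same mechanism, true −5; stronger dropout, about 25–50% missing per arm at week 96 | −4.7 to −4.0 | −3.8 to −1.9 | −5.1 to −5.0 |
| Same mechanism, no true effect | no bias beyond noise | no bias beyond noise | no bias beyond noise |
| Progression drives dropout in controls only, no true effect | +0.9 to +2.9 | +4.8 to +10.5 | within about 0.15 of 0 |

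Attenuation at about 25% missing is therefore 5 − 4.8 = 0.2 to 5 − 4.7 = 0.3 points (SD 5.7), or 5 − 4.3 = 0.7 to 5 − 3.6 = 1.4 points (SD 10.4). Under the stronger dropout it runs from 5 − 4.7 = 0.3 to 5 − 1.9 = 3.1 points.

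**5. Scale against noise.** In the moderate runs with change SD 10.4, the single-level estimates were −4.02 (SD 6.28) and −3.60 (SD 6.12). The bias is 0.98/6.28 = 0.16 and 1.40/6.12 = 0.23 of the estimate's own SD.

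**6. Precision.** With 50 patients the longitudinal model lowered the SD of the estimate from 6.27 to 6.24 (0.5%) at the low end, and from 6.64 to 5.89 (11%, dropout at random) at the high end. The gain is modest; the argument rests on bias.

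**7. Is the covariance choice important?** Week 96 was added to the random-intercept form of SAP 7.2, in single runs of 8,000 patients with controls-only dropout and no true effect. The single-level bias of 1.7 fell only to 0.7 (SD 5.7), and 8.6 only to 6.3 (SD 10). The unstructured model came to −0.35 and 0.12 in the same runs.

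**8. What stays unsolved.** When dropout depended on the unseen current score, the unstructured model was still biased by about 0.2 to 1.2 points (same mechanism, true effect 5) or 0.7 to 3.4 points (controls only, no effect).

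**The case against.** **Imputation is available.** The SAP nowhere prescribes a complete-case analysis, and a reader might infer from SAP 7.7 that all missing-data work is confined to the primary model. The text does not support that: only the predictors-of-missingness analysis is tied to that model, and imputation from all visits is open to any outcome. This stands. What remains is that imputation is discretionary and unassigned, so the default week-96 fit is on patients with a week-96 score.

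**The dropout premise is not in the documents.** A reader might infer that those who miss week 96 are mainly patients who progressed or died. No passage says so. Entry requires an anticipated survival of at least three years (Protocol 7.2), home visits may be offered at week 96 if staffing permits (Protocol 5.1), and patients taken off treatment for progression stay in follow-up (Protocol 8.8). These points reduce the risk without removing it. Missing totals could also exceed dropout: remote video visits under Protocol Appendix 2 leave two Part II items unrated, and SAP 9.1 requires every item for a total.

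**Status.** These are supportive or exploratory analyses in a Phase IIa pilot, and baseline-adjusted regression fits Protocol 11.4.3. This stands and limits the priority.

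**Small sample.** Unstructured covariance over five visits has 5 × 6 / 2 = 15 parameters with about 50 patients. This is fair, and calls for a fallback named in advance.

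**Conclusion.** The point holds for UMSARS I+II at week 96 as a conditional risk of bias. It needs two things: dropout that rises with observed worsening, and either a true effect or a mechanism that differs between arms. With a shared mechanism, a true 5-point effect and about 25% missing at week 96, the attenuation is about 0.2 to 0.3 points (change SD 5.7) or 0.7 to 1.4 points (change SD 10.4), and more if dropout is stronger. With no effect and the same mechanism in both arms there is no bias. The dropout rate, its link to progression and the size of the week-96 effect are all assumptions.

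A reader might extend these sizes to MoCA and UMSARS Parts III and IV. Nothing was computed for those scales, and SAP 9.1 defines no total for Parts III or IV. Nor does the point apply to MSA-QoL at week 48, which has no visit between baseline and that endpoint; at week 96 its only unused follow-up visit is week 48.

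This is a cheap improvement of modest priority.

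**What to change.** In SAP 7.4, give UMSARS I+II at week 96 its own analysis:

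- **Main analysis:** a repeated-measures model using weeks 12, 24, 36, 48 and 96, with treatment-by-visit terms, baseline score, MSA subtype and unstructured covariance, reporting the week-96 contrast. A commitment to multiple imputation from all visits is an acceptable alternative.
- **Fallback:** name it now. Multiple imputation from all visits is suitable. The random-intercept form of SAP 7.2 is not, because it leaves much of the bias (step 7 of the working).
- **Sensitivity analysis:** keep the single-level regression.
- **Other scales:** the same approach can be used for MoCA, and for UMSARS III and IV where a numerical score suits it.
- **Limits:** state that neither method resolves deaths before week 96 or dropout that depends on unseen scores.

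The cost is a paragraph of SAP text and a little code. The downside is more variance parameters with about 50 patients. No visit, assessment or sample size changes.

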## 7.5 Sensitivity analyses

Several sensitivity analyses will be performed for the primary outcome. These are:

- The effect of the intervention will be assessed using a single-level linear regression model, adjusted for MSA subtype and baseline severity.
- If adherence is deemed to be an issue, per-protocol and complier average causal effect (CACE) analyses will be performed.

## 7.6 Subgroup analyses

There are no planned subgroup analyses.

## 7.7 Missing data

Withdrawals from the study, loss to follow up and other missing outcome data will be summarised separately by randomised arm. Potential bias due to missing data will be investigated by comparing the baseline characteristics of patients with and without missing values. From this, predictors of missingness may be identified and used to perform an additional analysis that includes these predictors as covariates in the primary analysis model.

Multiple imputation may also be performed, if deemed appropriate. The imputation model will include outcome data from all time-points, as well as baseline characteristics.

In addition, imputation may be performed under the assumption that the missing data are MNAR. Two strategies may be investigated:

- Delta-adjustment: This approach initially uses (standard) multiple imputation to impute missing values but then the imputed values are modified using a ‘delta-adjustment’. Different values of delta may be specified, and these can differ by trial arm.
- Reference-based sensitivity analyses: A range of different assumptions regarding the missing data can be investigated using this approach, which is implemented in the Stata package mimix (Cro et al, 2016).

## 7.8 Adverse event reporting

The number, nature and severity of serious adverse events (if any) will be reported separately by study arm at each follow up time point. The number of patients who experience adverse events will likewise be reported separately by study arm.

## 7.9 Software

All the statistical analysis will be performed using Stata version 17 (or above).

# 8 Summary of Changes

This Statistical Analysis Plan does not propose any major changes to the statistical approach described in the protocol. Of note, is that the primary analysis proposed in this document uses outcomes from four time-points; however, the effect of intervention will still be estimated at 48 weeks. Any changes to the Statistical Analysis Plan made after this document has been signed off need to be recorded. In addition, significant changes will need to be approved before implementation.

## 9 Appendix - Questionnaires scoring

### 9.1 The Unified Multiple System Atrophy Rating Scale (UMSARS) score

The Unified MSA Rating Scale (UMSARS) comprises four components: a historical review of disease-related impairments (Part I, 12 items), motor examination (Part II, 14 items), autonomic examination (Part III), and global disability scale (Part IV). A single score using a 0 (no impairment) to 4 (severe impairment) scale was generated for each item. UMSARS total is calculated as the sum of the Part I and Part II items; all items must be answered to have a score.

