8.4 Subsequent assessments and procedures

Week 4 (+/-1 week) – telephone call

The study nurse will call the participants to ensure the participants are taking their medication according to the protocol requirements and completing their trial diary as required. They will also perform a concomitant medication and AE check.

Week 12 assessments – Visit 3

At 12 weeks after baseline evaluation, each patient will be telephoned 1 week prior to remind them of their visit

Participants will attend the research centre for the following trial procedures:

- Physical Examination (if deemed necessary by trial clinician for clinical purposes)
- Routine blood tests (FBC, U&E, LFT, glucose, amylase, HbA1c, PT and APTT)
- Serum collection
- Vital signs including weight
- UMSARS Part II (videotaped)
- UMSARS Part I, III and IV
- The Unified Dystonia Rating Scale
- MoCA
- Timed Motor tests
- BDI-II
- Concomitant Medications review
- Adverse Events review
- Dispensing of 12 exenatide (Bydureon or Bydureon BCise) pens (if randomised to receive exenatide).

All participants will be invited for face to face visits at all timepoints. If a participant is unable or unwilling to attend any of the follow up assessments (12,24,36,48,96 weeks), they may be offered the option of a home visit by one or more members of the trial clinical team if staffing levels permit. These participants will be asked to consent to home visits. Assessments will be performed as per protocol. Weight will be measured only if the participant is able to stand, and weighing scales are available. Dispensing of IMP will be performed by trial pharmacy and transported to the patient in an appropriate Cool Bag with temperature logger by the clinical trial team.

Week 24 assessments – Visit 4

At 24 weeks after baseline evaluation, each patient will be telephoned 1 week prior to remind them of their visit. They will be asked not to have eaten and to have drunk water only for 6 hours to enable fasting blood samples to be taken.

Participants will attend the research centre for the following trial procedures:

- Physical Examination (if deemed necessary by trial clinician for clinical purposes)
- Neurological Examination (if deemed necessary by trial clinician for clinical purposes)
- Fasting blood tests (FBC, U&E, LFT, glucose, amylase, insulin, c-peptide, HbA1c)
- Serum collection
- Vital signs including weight
- UMSARS Part II (videotaped)

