Appendix 1 - Schedule of assessments

1. Medical History: including MSA history, family history, medication history, previous imaging, previous genetic tests and previous drug compliance issues.
2. Vital signs: blood pressure, respiratory rate, heart rate, temperature, oxygen saturation and weight.
3. Routine blood tests: FBC, U&E, LFT, glucose, amylase, HbA1c, PT and APTT (PT and APTT not done at weeks 24 and 36).
4. Fasting blood tests
 - Baseline visit: glucose, insulin, c-peptide, and triglycerides.
 - Week 24 visit: glucose, insulin, c-peptide.
 - Week 48 visit: glucose, insulin, c-peptide.
5. 5 IMP administration: Participants will be randomly allocated into 2 groups to receive either Exenatide (n[~]=25) or best medical treatment (n[~]=25). Only participants randomised to the Exenatide arm will receive the IMP.
 6. At Week 4 the study nurse will call the participants to provide support and optimise compliance.
 7. At Week 58 the study nurse will call the participants to perform an adverse event check.

8. Randomisation will occur once eligibility has been confirmed prior to Visit 2 to allow Pharmacy team time to prepare IMP for dispensing.
9. * Clinical and Neurological examinations will be performed with deemed relevant/necessary by trial clinician for clinical purposes.
10. Only a serum sample will be collected for research purposes at week 96.

Appendix 2

COVID19 mitigation plans

The objective of this Appendix is to set out a plan detailing the proposed continuation of the Exenatide-MSA trial if a restriction in trial Face to Face visits should occur as a result of a resurgence of COVID19 infections.

CONTINUATION OF IMP DISPENSING FOR EXISTING TRIAL RECRUITS

1. Patient consent required. Each patient will be contacted by the research team, at site. Consent to ship IMP to the patients home to be fully documented in source notes
2. Patient will be assessed via telephone by Chief Investigator (or appropriate delegated trial team member) to decipher whether suitable to dispense IMP. Specific questions to be asked in relation to abdominal pain/ weight/ AEs/ new con-meds etc.

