3. NB Scheduled blood tests will not be performed. Given that Exenatide is licensed for the treatment of Type 2 Diabetes that does not routinely require regular monitoring of patient safety using blood tests, these will not be performed unless a patient describes symptoms potentially indicating an adverse effect of the IMP. In the event of a clinically significant adverse reaction to the IMP, dispensing will be paused until a face to face evaluation of the participant can be completed.
4. If a patient describes adverse events that require urgent medical treatment, appropriate clinical advice will be given to patient regarding all/ any necessary precautions/ investigations/ treatment options through trial team/ GP/ local hospital facilities.

If it is deemed suitable to dispense IMP:

- A) Consent for telephone follow-up and IMP delivery obtained verbally and documented (as per MHRA/ HRA advice)
- B) IMP prescribed by trial team (as normal)
- C) Courier collects IMP from NHNN Pharmacy
- D) Upon arrival at participants address courier has agreed to unpack the IMP from cooler, wipe them down (alcohol wipe), place at the patients door and ring and then step back (to minimise COVID-19 transmission risk). Patients will be informed by site team when to expect the delivery.
- E) The site team shall then call the patient and confirm and document delivery.

REMOTE ASSESSMENTS

To minimise disruption to the scientific integrity of the trial, for patients who remain well but who are unable to attend a scheduled trial visit due to National guidelines/ patient concerns regarding risk of travel, face to face evaluation will be replaced by remote evaluation. Questionnaires will be completed remotely and a Video examination of UMSARS part 2 will be performed with the exception that Rigidity will not be rated (Item 6), and the Pull test will not be performed (Item 13) . These remote measures will be appropriately labelled to ensure that any necessary adjustments for remote/ face to face assessments are incorporated in the final statistical analysis of the trial.

Visit CRFs will otherwise be completed in full. The fact that this visit has taken place by video/ telephone will be documented on paper CRF and source notes along with all relevant visit information.

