#### 7.1.2 Secondary outcomes

- Patients with loss of independent ambulation by the end of the study, defined by a score of 4 in UMSARS-I item 7 (walking);
- Multiple System Atrophy health-related Quality of life (MSA-QoL) scale at week 48;
- UMSARS score (Parts III and IV) at week 48;
- Anti-parkinsonian or anti-orthostatic hypotension drugs comparing exenatide at week 48;
- The number of falls at week 48;
- Patients reaching a score of 3 or more on UMSARS-I items 1 (speech), 2 (swallowing), and 8 (falling) at week 48;
- Clinical global impression (CGI) at week 48;
- Montreal Cognitive Assessment (MoCA) scores at week 48;
- Safety of exenatide in MSA based on Adverse event reporting.

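### The all-items rule for the UMSARS total leaves no primary endpoint value at a week-48 video visit, because two Part II items are omitted there by design

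*SAP*

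**What the plan says.** SAP 7.1.1 defines the primary outcome as the UMSARS total (Parts I and II) at 48 weeks. SAP 9.1 gives Part I 12 items and Part II 14 items, each scored 0 to 4, and sets the scoring rule: "UMSARS total is calculated as the sum of the Part I and Part II items; all items must be answered to have a score".

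Protocol Appendix 2 is a contingency plan, to be used "if a restriction in trial Face to Face visits should occur as a result of a resurgence of COVID19 infections". For patients who are well but cannot attend because of national guidance or worry about travel, a remote evaluation replaces the face-to-face one. Part II is then examined by video, "with the exception that Rigidity will not be rated (Item 6), and the Pull test will not be performed (Item 13"). The rest of the visit form is completed. No visit is exempt, so week 48 is included. The appendix adds: "These remote measures will be appropriately labelled", so that "any necessary adjustments for remote/ face to face assessments are incorporated in the final statistical analysis of the trial".

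The SAP does not take this up:

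- The primary model (7.2) uses totals from weeks 12, 24, 36 and 48 and has no visit-mode term.
- The sensitivity analyses (7.5) do not mention remote visits.
- The missing-data section (7.7) makes multiple imputation optional, using outcome data from all time-points and baseline characteristics, and says nothing about single items.
- For MSA-QoL, by contrast, SAP 9.2 does have a rule for partly completed questionnaires.

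**The concern.** The two documents do not fit together. The protocol plans for visits at which two Part II items are left out, and the SAP scoring rule then discards the whole total. At week 48 that total is the primary endpoint. The 24 rated items from the same visit, which are the best predictors of the missing total, are not used for it.

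The loss is confined to the total. Single Part I items from a video visit can still feed the secondary outcomes on walking and on "Patients reaching a score of 3 or more on UMSARS-I items 1 (speech), 2 (swallowing), and 8 (falling) at week 48". In-person home visits are not affected, because Protocol 8.4 says of them: "Assessments will be performed as per protocol".

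The sample size leaves little room for a further loss at week 48, since the increase from 40 to 50 is already used for dropout: "Based on a 20% dropout rate as reported from previous trials, the sample size would be 50 (25 per arm"). The protocol also promises an adjustment that the SAP never defines. If video visits occurred, the analyst must either drop valid ratings or choose a method after the data are in, in an open-label trial.

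**Working it through.** **Items.** 12 + 14 = 26 items, maximum 26 × 4 = 104. A video visit omits 2, so 24 are rated, maximum 24 × 4 = 96. The all-items condition fails and there is no total.

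**The plan's own sample size (SAP 4.3).** Inputs: difference 5, SD 10.4, baseline–final correlation 0.85, two-sided 5%, 80% power, 20% dropout.

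- Residual SD = 10.4 × √(1 − 0.85²) = 5.48.
- With 20 per arm, SE = 5.48 × √(2/20) = 1.73, and power by the noncentral t distribution is 80.2%.
- 40 / 0.8 = 50. The plan's figures are reproduced.

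**Assumptions from here on.** The documents give no number of video visits. I take 0, 10, 20 or 30% of week-48 visits by video. For the mixed model I take a compound-symmetry correlation c of 0.5 or 0.7 between visits after baseline adjustment, separate arm means at each visit, and generalised least squares for the standard error.

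**Single-level model (the SAP 7.5 sensitivity analysis), from 40 evaluable.** SE = 5.48 × √(2/n):

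| Video share | n per arm | SE | Power |
|---|---|---|---|
| 0% | 20 | 1.73 | 80.2% |
| 10% | 18 | 1.83 | 75.6% |
| 20% | 16 | 1.94 | 70.3% |
| 30% | 14 | 2.07 | 64.0% |

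**Primary mixed model.** Base 40 has 20 per arm with weeks 12 to 36 complete. Base 50 has 25 per arm, of whom 5 drop out after week 36 but still supply the earlier visits, which is optimistic. The share applies to the 20 per arm who remain at week 48.

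| Video share | Base 40, c = 0.5: SE, power | Base 40, c = 0.7: SE, power | Base 50, c = 0.5: SE, power | Base 50, c = 0.7: SE, power |
|---|---|---|---|---|
| 0% | 1.732, 80.2% | 1.732, 80.2% | 1.666, 83.6% | 1.623, 85.5% |
| 10% | 1.792, 77.5% | 1.769, 78.5% | 1.728, 80.9% | 1.662, 83.8% |
| 20% | 1.863, 74.3% | 1.814, 76.5% | 1.801, 77.6% | 1.710, 81.7% |
| 30% | 1.951, 70.3% | 1.871, 73.9% | 1.892, 73.5% | 1.770, 79.0% |

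**One week-48 video visit per arm.** Base 40: 80.2% falls to 78.9% (c = 0.5) or 79.4% (c = 0.7). Base 50: 83.6% falls to 82.3%, or 85.5% to 84.7%.

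**Earlier visits.** If 30% of totals are missing at weeks 12 to 36 but every patient has week 48, the SE of the week-48 effect stays at 1.732 for both values of c. With the 20% dropout of base 50 and c = 0.5, it moves only from 1.666 to 1.670. The cost comes from week 48.

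**Imputing only the two items.** Let s be the SD of each omitted item given the rated ones (assumed 0.5 to 1.0) and r the video share. In the single-level model with 20 per arm, the variance of the effect is 2 × [5.48² + r/(1 − r) × 2s²] / 20. Power at r = 10, 20 and 30% is 80.1, 80.0 and 79.9% for s = 0.5, and 79.9, 79.5 and 79.1% for s = 1.0. Almost all of the loss is avoidable.

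**The case against.** The strongest reply is that this is contingent. Appendix 2 applies only under COVID restrictions, neither document reports a video visit, and every share, correlation and item SD above is assumed. Patients who cannot attend may be offered a home visit with the full scale, if staffing allows. A missing week-48 total does not remove the patient from the mixed model, and SAP 7.7 offers imputation. The trial collects pilot data, and a precision loss of unknown and possibly zero size is small beside the uncertainty in the planning SD and correlation.

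Much of that stands, and it limits the size of the problem. It does not remove the conflict. Home visits are optional and could be restricted by the same circumstances. The tables for the mixed model already count the earlier visits. SAP 7.7 works on scores and is discretionary, so it does not call on the 24 items rated that day.

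Two points about the remedy also stand. Imputing within arm from 24 items plus adjacent visits would ask too much of 14 to 20 week-48 donors per arm, so the imputation model must be kept small. The 79% to 80% after imputation treats the two items as independent given the rest and omits part of the uncertainty in the imputation model, so it is a best case.

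**Conclusion.** The concern holds and should be fixed before analysis. As written, a week-48 video visit under Appendix 2 yields no primary endpoint value, and the SAP contains neither a rule for the two omitted items nor the adjustment that the protocol promises. The consequence is lost precision on the primary outcome. No bias or imbalance between arms is shown.

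The size depends on a number that the documents do not give. Under the assumed shares of 10 to 30%, the primary analysis loses about 2 to 10 points of power, depending on the share, the correlation and the starting number of patients. The single-level sensitivity model loses about 5 to 16 points. If no video visit took place, the results are unaffected.

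**What to change.** Amend SAP 9.1 before analysis.

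1. If any Appendix 2 video visits occurred, impute items 6 and 13 at those labelled visits by item-level multiple imputation, then form the 26-item total. Put arm in a parsimonious imputation model that draws on the patient's other rated items and adjacent face-to-face visits; summary scores in place of all 24 items would keep it small. Keep the all-items rule in every other case.
2. Add one sensitivity analysis: the primary model on the common 24-item total (range 0 to 96) for all patients at all visits.
3. Add a visit-mode covariate only if there are enough video visits to estimate it, and fix the minimum number in advance.
4. If there were no video visits, state that and leave the rule as it is.

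The cost is SAP wording, recorded as SAP section 8 requires (and approved, if judged significant), and some programming. No new data are needed, since remote measures are already labelled. There are two drawbacks: a missing-at-random assumption for two items, and a 24-item score that is not on the scale of the 5-point target difference, which is why it belongs in a sensitivity analysis.
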